3.2. Study Periods and Visits for Each Patient

The study periods / visits described in this section are defined for all patients, and summarized in Figure 3. Please note:

• For all patients, the Safety Assessment Period begins at the time the informed consent form (ICF) is signed for the study (that is, the beginning of the Screening Period) and continues until at least 30 days after the last day of study therapy (that is, the end of the Safety Follow-up Period). After the 30-day Safety Follow-Up Visit (see below), patients will be assessed for drug-related serious adverse events (SAEs) only.

• For each patient, the Study Duration is defined as the time from day of ICF signature to the last day of Disease Assessment Follow-up / Survival Follow-up (see below).

No protocol-specific procedures or assessments may be performed prior to completion of the ICF, except for those that represent standard-of-care.

Abbreviations: C=Cycle; D=Day; d=days; EOT=end-of-treatment; FU=follow-up; PD=progressive disease: Tx=treatment.

Figure 3. Overview of study periods and visits

3.2.1. Screening Period

The Screening Period is defined as the time from the time the patient completes the ICF form until the date and time of first dose of study therapy. Unless otherwise described in the Schedule of Events (Table 1), all screening assessments must be performed within 28 days prior to the first dose of study therapy.

Determination of eligibility is based on the entry criteria enumerated in Section 4, including determination of FGFR1 or FGFR2 amplification status per the methods described in Section 6.1.1 of this protocol.

3.2.2. Patient Enrollment

Once the ICF is signed, the patient will be assigned a unique patient identification number. Once study eligibility is confirmed, the patient will be enrolled into the appropriate treatment cohort.

3.2.3. Treatment Period and End of Treatment Visit

Treatment discontinuation may occur for any of the reasons listed in Section 4.4. The treatment period is the time from the date of first dose of study therapy (Day 1) to the date of last dose of study therapy. An end-of-treatment (EOT) visit must be performed within 7 days after the decision is made to discontinue study treatment; at this visit, every effort should be made to perform the assessments outlined in Table 1. For patients who discontinue at a planned study visit, that visit may be considered the EOT visit if all assessments required at EOT are performed.

3.2.4. Safety Follow-Up Period and 30-Day Safety Follow-Up Visit

The safety follow-up period is the time from the date of last dose of study therapy through the 30-day safety follow-up visit, which must be performed 30 days (±3 days) following the last dose of study therapy. If the patient starts new anticancer therapy within 30 days of the last dose of TAS-120, the 30-day safety follow-up visit should be performed before the start of new anticancer therapy. Every effort should be made to perform the assessments outlined in Table 1. If the patient is unable to return to the study site, a follow-up phone call can be made by the study site to collect any new safety information that occurred during the Safety Follow-up Period.

After the 30-day Safety Visit, only AEs that are serious and drug-related will be assessed.

3.2.5. Post-Discontinuation Disease Assessment

Patients who discontinue without documented disease progression should continue to undergo tumor assessments/scans according to the Schedule of Events (that is, every 12 weeks ± 7 days until progressive disease (PD) is documented, new anticancer therapy is initiated, the study is terminated, or the patient dies, withdraws consent, or is lost to follow-up).

3.2.6. Survival Follow-Up

Once disease progression is confirmed or the first subsequent new breast cancer therapy is initiated, whichever occurs first, the survival follow-up period begins. During this period, the patient or family should be contacted for survival follow-up every 12 weeks (±2 weeks) until withdrawal of consent, death, or loss to follow up, until survival events (deaths) have been reported for 75% of enrolled patients or the study is terminated earlier by the Sponsor. In addition, all subsequent breast cancer treatments will be recorded.

3.3. Study Completion and Study Extension

The study will be considered complete when:

- Survival events (deaths) have been reported for 75% of enrolled patients; or
- The trial is halted early for any reason.

Following Study Completion, patients still receiving and deriving benefit from study therapy in the opinion of the Investigator and Sponsor will be permitted to continue treatment in a Study Extension phase. During the Study Extension, patients may receive treatment until withdrawal criteria are met. During this period, limited information will be collected as follows (including but not limited to):

- Study drug administration;
- Study drug accountability;
- Serious adverse events;
- Non-serious adverse events that are related to study treatment or result in treatment discontinuation; and
- Any cases of pregnancy, overdose, or medication error.

3.4. Randomization and Blinding

This is an open-label, non-randomized study.

4. SELECTION AND WITHDRAWAL OF PATIENTS

Determination of *FGFR* amplification status should be completed before the patient undergoes any other protocol-specific procedures. Patients must have either HR+ HER2- breast cancer or TNBC harboring an *FGFR2* amplification, or HR+ HER2- breast cancer harboring an *FGFR1* high-level amplification (Section 6.1.1).

Waivers will not be granted for any of the eligibility criteria.

4.1. Inclusion Criteria

A patient must meet all of the following inclusion criteria to be eligible for this study.

- 1. Patient provides written informed consent.
- 2. Patient is ≥18 years of age (or meets the country's regulatory definition for legal adult age, whichever is greater)
- 3. Eastern Cooperative Oncology Group (ECOG) performance status 0 or 1.
- 4. Histologically or cytologically confirmed recurrent locally advanced or metastatic breast cancer not amenable to treatment with curative intent, meeting all of the criteria for 1 of the following cohorts:

A. Cohort 1

- i. HR+ HER2- breast cancer harboring an *FGFR2* gene amplification. HR+ HER2- breast cancer is defined per the local pathology report as estrogen receptor (ER) >1% and/or progesterone receptor (PR) >1%, HER2-negative per American Society of Clinical Oncology (ASCO) and the College of American Pathologists (CAP) guidelines, 2018.
- ii. Measurable disease per Response Evaluation Criteria in Solid Tumors (RECIST) Version 1.1
- iii. Has received 1-3 prior endocrine-containing therapies and up to 2 prior chemotherapy regimens for advanced/metastatic disease
- iv. Has received prior treatment with a CDK4/6 inhibitor or is ineligible for such treatment (per Investigator decision)
- v. Has experienced disease progression/recurrence within 1 month following the completion of any endocrine therapy for advanced/metastatic breast cancer

B. Cohort 2

- i. TNBC harboring an *FGFR2* gene amplification. TNBC is defined as negative for ER, PR and HER2. Negative for ER and PR includes the following: local pathology report classifies them as negative, Allred Score of 2 or below or <1% staining. HER2-negative per ASCO / CAP guidelines, 2018.
- ii. Measurable disease per RECIST 1.1
- iii. Has received at least 1 prior chemotherapy or chemotherapy/immunotherapy (PD-L1/PD-1 inhibitors) regimen for advanced/metastatic disease
- iv. Has experienced disease progression/recurrence during or after the most recent prior chemotherapy for advanced/metastatic breast cancer

C. Cohort 3

- i. TNBC or HR+ HER2- breast cancer (defined as above) harboring an *FGFR2* gene amplification
- ii. Non-measurable, evaluable disease per RECIST 1.1. Patients with bone-only disease must have lytic or mixed lytic-blastic lesions
- iii. Other criteria for either HR+ HER2- breast cancer or TNBC should be met as described for Cohort 1 and 2, respectively

D. Cohort 4

- i. HR⁺ HER2⁻ breast cancer (defined as above) harboring an *FGFR1* high-level gene amplification as defined in Section 6.1.1.1
- ii. Measurable disease per RECIST 1.1
- iii. Has received 1-2 prior endocrine-containing therapies and no more than 1 prior chemotherapy regimen for advanced/metastatic disease. Prior treatment with fulvestrant is not permitted.
- iv. Has received prior treatment with a CDK4/6 inhibitor or is ineligible for such treatment (per Investigator decision)
- v. Pre/peri-menopausal patients must be on goserelin. Patients must have commenced treatment with goserelin or an alternative GnRH agonist at least 4 weeks prior to the first dose of fulvestrant. If patients have received an alternative GnRH agonist prior to study entry, they must switch to goserelin for the duration of the trial. Postmenopausal is defined as at least one of the following criteria: age ≥60 years; age <60 years and cessation of regular menses for at least 12 consecutive months with no alternative pathological or physiological cause; and serum estradiol and follicle-stimulating hormone level within the laboratory's reference range for postmenopausal females; or documented bilateral oophorectomy.
- vi. Has experienced disease progression/recurrence within 1 month following the completion of any endocrine therapy for advanced/metastatic breast cancer.
- 5. Archival or (preferably) fresh tumor tissue must be available for central laboratory confirmation of *FGFR* amplification.
- 6. The patient is able to take medications orally (a feeding tube is not permitted).
- 7. The patient has adequate organ function as defined by the following criteria:
 - a. Aspartate aminotransferase (AST) and alanine aminotransferase (ALT) \leq 3.0 × the upper limit of normal (ULN); if liver function abnormalities are due to underlying liver metastases, AST and ALT \leq 5 × ULN
 - b. Total bilirubin $\leq 1.5 \times \text{ULN}$ or $\leq 3 \times \text{ULN}$ in case of Gilbert's syndrome
 - c. Absolute neutrophil count (ANC) \geq 1.0 × 10 9 /L without hematopoietic growth factor support
 - d. Platelet count \geq 75 × 10⁹/L without transfusion support (that is, excluding measurements obtained within 3 days after transfusion of platelets)
 - e. Hemoglobin ≥9.0 g/dL without transfusion support (that is, excluding measurements within 7 days after transfusion of packed red blood cells or whole blood)
 - f. Serum phosphorus \leq ULN

- g. Creatinine clearance (calculated or measured value): ≥40 mL/min
- 8. Women of child-bearing potential (WOCBP) must have a negative serum pregnancy test prior to administration of the first dose of TAS-120. Female patients are not considered to be of child-bearing potential if they have a history of hysterectomy or are post-menopausal, defined as above. Both males and females of reproductive potential must agree to use effective birth control during the study prior to the first dose and for 90 days after the last dose of TAS-120 and 1 year after last dose of fulvestrant (Cohort 4 only).
- 9. The patient is willing and able to comply with scheduled visits and study procedures.

4.2. Exclusion Criteria

A patient must not meet any of the following exclusion criteria to be eligible for this study:

- 10. History and/or current evidence of any of the following disorders:
 - a. Non-tumor related alteration of the calcium-phosphorus homeostasis that is considered clinically significant in the opinion of the Investigator
 - b. Ectopic mineralization/calcification, including but not limited to soft tissue, kidneys, intestine, or myocardia and lung, considered clinically significant in the opinion of the Investigator
 - c. Retinal or corneal disorder confirmed by retinal/corneal examination and considered clinically significant in the opinion of the Investigator.
- 11. Corrected QT interval using Fridericia's formula (QTcF) >470 msec. Patients with an atrioventricular pacemaker or other condition (for example, right bundle branch block) that renders the QT measurement invalid are an exception and the criterion does not apply.
- 12. Treatment with any of the following within the specified time frame prior to the first dose of TAS-120:
 - a. Major surgery within 4 weeks (the surgical incision should be fully healed)
 - b. Radiotherapy for extended field within 4 weeks or limited field radiotherapy within 2 weeks
 - c. Any prior systemic therapy regardless of the stop date, but the patient must have recovered to eligibility levels from prior toxicity
 - d. Any investigational agent received within 30 days or 5 half-lives (whichever is shorter)
- 13. Prior treatment with an FGFR inhibitor
- 14. **Cohort 4 only:** Prior treatment with fulvestrant, or known hypersensitivity to fulvestrant.
- 15. A serious illness or medical condition(s) including but not limited to the following:
 - a. Known acute systemic infection
 - b. Myocardial infarction, severe/unstable angina, or symptomatic congestive heart failure within the previous 6 months
 - c. History or current evidence of serious uncontrolled ventricular arrhythmia
 - d. Chronic diarrhea diseases considered to be clinically significant in the opinion of the Investigator

- e. Congenital long QT syndrome, or any known history of torsade de pointes, or family history of unexplained sudden death
- f. Other severe acute or chronic medical or psychiatric condition or laboratory abnormality that may increase the risk associated with study participation or TAS-120 administration, or may interfere with the interpretation of study results, and in the judgment of the Investigator would make the patient inappropriate for entry into this study
- 16. Brain metastases that are untreated or clinically or radiologically unstable (that is, have been stable for <1 month)
- 17. History of another primary malignancy that is currently clinically significant or currently requires active intervention
- 18. Pregnant or lactating female

4.3. Screen Failure

Screen failures are defined as patients who consent to participate in any portion of the clinical study but are not subsequently enrolled in the study. A minimal set of screen failure information is required to ensure transparent reporting of screen failure patients to Regulatory Authorities. Minimal information includes demography, screen failure details, eligibility criteria, and any SAE occurring after completion of the ICF. Patients who do not meet the criteria for participation in this study (screen failure) may be rescreened a maximum of 2 times.

4.4. Discontinuation of Treatment

A patient may be discontinued from all study therapy for any of the following reasons:

- 1. Disease progression based on RECIST 1.1;
- 2. Clinical disease progression per Investigator judgement;
- 3. Unacceptable AEs, or change in underlying condition such that the patient can no longer tolerate therapy, as evidenced by a dose delay > 28 days from the scheduled start date of the next cycle or need for more than the allowable number of dose reductions outlined in this protocol;
- 4. Physician's decision, including need for other anticancer therapy not specified in the protocol, or surgery or radiotherapy to the only site(s) of disease being followed in the study;
- 5. Pregnancy;
- 6. A significant protocol deviation which, in the opinion of the Investigator and/or Sponsor, renders the patient unsuitable for further study treatment;
- 7. Loss to follow-up;
- 8. Death;
- 9. Termination of the study by the Sponsor; or
- 10. At the patient's request at any time irrespective of the reason.

Patients who withdraw consent for further treatment (treatment discontinuation criterion #10) may choose to remain on study; in such a case, all study evaluations should continue as outlined in this protocol. If the patient withdraws consent to all follow-up, the patient should be considered to have discontinued the study as described in Section 4.5.

The primary reason for discontinuation should be documented in the electronic case report form (eCRF).

If there is strong evidence of clinical benefit and reasons to justify continuation of the study drug, even though treatment discontinuation criteria have been met, this decision must be reviewed with the Sponsor on a case-by-case basis, and continuation of therapy may be allowed assuming all other treatment resumption criteria have been met.

4.5. Discontinuation from the Study

A patient may be discontinued from all study interventions and assessments (that is, discontinued from the study without follow-up) for any of the following reasons:

- 1. Death;
- 2. Loss to follow-up / contact despite best effort of investigative site personnel (that is, after at least 2 documented attempts to contact the patient and/or family); or
- 3. Patient withdrawal of consent to further follow-up, irrespective of the reason.

5. STUDY TREATMENT

5.1. Study Drug Administration

5.1.1. TAS-120

A treatment cycle is defined as 28 days; however, TAS-120 is dosed continuously every day with no planned interruption between cycles.

TAS-120 is supplied as 4-mg tablets and will be taken PO at a dose of 20 mg QD in Cohorts 1, 2, and 3. In Cohort 4, TAS-120 will be taken PO at a dose of 20 or 16 mg QD, depending on the DLT observations in the safety lead-in phase.

TAS-120 should be taken under fasting conditions. It will be taken with a glass of water, on an empty stomach, every 24 hours in the morning or evening at the same time each day, if possible. No food should be consumed for 2 hours prior and 1 hour after the dose of TAS-120, but patients will be permitted to drink water during this period.

In the event of a dosing delay up to 12 hours after the scheduled dosing time, the patient should still take that day's dose. If the dosing delay continues for >12 hours after the scheduled dosing time, or if the patient vomits after a dose, the patient should skip dosing for that day and not make up for it the following day.

Please note: dietary restrictions that limit phosphate intake may reduce the risk of hyperphosphatemia (Appendix B).

5.1.2. Fulvestrant

Fulvestrant (Faslodex®) will be administered to patients in Cohort 4 only according to the approved commercial labeling.

Fulvestrant 500 mg will be administered IM into the buttocks (gluteal area), slowly (1-2 minutes per injection), as two 5-mL injections, one in each buttock, on Days 1 and 15 of Cycle 1, then Day 1 every subsequent cycle thereafter (every 28 days \pm 3 days).

Pre/peri-menopausal patients in Cohort 4 are required to also have ovarian suppression with goserelin as part of standard of care, having started a GnRH analogue at least 4 weeks prior to the first dose of fulvestrant.

5.1.3. Treatment Duration

There is no predefined duration of treatment. In all cohorts, study therapy may continue until disease progression, unacceptable toxicity, or any other criteria for treatment discontinuation is met (see Section 4.4).

5.2. Definition of a Dose-Limiting Toxicity (Cohort 4 Only)

For patients in the safety lead-in portion of Cohort 4 only, a DLT is defined as any AE that is not clearly attributable to an extraneous cause, such as an underlying disease, occurring in Cycle 1 and meeting at least one of the following criteria (Table 3).

Table 3: Dose Limiting Toxicity Definition

	Grade 4 neutropenia lasting >7 consecutive days	
Hematologic Toxicity	Grade 4 thrombocytopenia lasting >7 consecutive days	
	≥ Grade 3 thrombocytopenia with bleeding	
	Febrile neutropenia (ANC <1000/mm³ with a single body temperature of >38.3°C [101°F] or a sustained temperature of ≥38°C [100.4°F] for more than 1 hour) requiring initiation of antibiotics	
	Grade 3 total bilirubin lasting >7 consecutive days	
	Grade 4 total bilirubin	
	Grade 3 AST and/or ALT lasting >7 consecutive days	
	Grade 4 ALT and/or AST lasting >3 consecutive days	
Henotic Toxicity ^a	For patients with liver metastases, AST or ALT $>$ 8 × ULN or AST or ALT $>$ 5 × ULN lasting \ge 14 consecutive days	
Hepatic Toxicity ^a	Hy's Law criteria - concurrent observation of the following, with no other reason found to explain the findings (such as viral hepatitis A, B, or C; preexisting or acute liver disease; or another drug capable of causing the observed liver injury):	
	• Elevated aminotransferase enzymes of >3 × ULN	
	• Alkaline phosphatase (ALP) <2 × ULN	
	• Associated with an increase in bilirubin $\ge 2 \times ULN$	
Renal Toxicity	Creatinine clearance <30 mL/min for >3 days despite optimal supportive care	
Other Non-Hematologic Toxicity	≥ Grade 3 ^b	
	Any toxicities leading to a TAS-120 Cycle 1 dose intensity of <75% and/or fulvestrant dose intensity of <100%	
Other	Inability to initiate Day 1 of Cycle 2 within 14 days of schedule due to any continuously ongoing Grade \geq 2 toxicity	
	Any death not clearly attributed to the underlying disease or extraneous causes	

Abbreviations: ALP=alkaline phosphatase; ALT=alanine aminotransferase; ANC=absolute neutrophil count; AST=aspartate aminotransferase; ULN=upper limit of normal.

- a. For any Grade 3 or 4 hepatic toxicity not resolved within 7 days to Grade 0 1 (or Grade 2 if liver metastases), an abdominal computed tomography scan should be performed to assess if it is related to disease progression.
- b. The following events will not be considered DLTs:
 - Nausea, vomiting and diarrhea (unless they persist to be Grade ≥3 for >3 consecutive days despite optimal supportive care)
 - Hyperphosphatemia (unless it persists to be Grade ≥3 for >7 consecutive days despite optimal phosphatelowering therapy)
 - Fatigue (unless it is lasting ≥1 week).
 - Asymptomatic Grade ≥3 electrolyte abnormality (unless it is lasting >72 hours). For patients with clinical symptoms, however, all Grade ≥3 electrolyte abnormalities regardless of duration will be considered a DLT.
 - Grade ≥3 amylase or lipase elevation not associated with symptoms or clinical manifestations of pancreatitis.

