Cohorts 1 and 2 will initially enroll a total of approximately 19 response-evaluable patients per cohort. If \geq 4 responses (PR or CR) are observed in a cohort, that cohort will be further expanded to a total of approximately 55 response-evaluable patients.

Cohort 3 will initially enroll a total of approximately 9 response-evaluable patients. If ≥ 3 patients experience clinical benefit (CR, or SD ≥ 24 weeks) are observed, the cohort will be further expanded to a total of approximately 24 response-evaluable patients.

Because the combination of TAS-120 and fulvestrant has not been assessed in patients, **Cohort 4** will begin with a safety lead-in period. During the safety lead-in, 3 patients will initially be enrolled and will receive TAS-120 (20 mg QD) and fulvestrant (500 mg) according to the study schedule, with safety follow-up of at least 1 cycle. Patients will be assessed for DLTs and the recommended dose of TAS-120 for this cohort will be determined as follows.

- Of the initial 3 patients, if 0/3 or 1/3 patients present with a DLT, another 3 patients will be enrolled.
 - o If 0/6 or 1/6 patients present with a DLT, the safety lead-in phase will conclude and enrollment will continue to a total of 28 patients treated with TAS-120 (20 mg QD) plus fulvestrant.
- If ≥2/3 or ≥2/6 patients present with a DLT, TAS-120 20 mg QD plus fulvestrant will be defined as a non-tolerated dose level for the combination. Subsequent patients will be treated at a dose of TAS-120 of 16 mg QD plus fulvestrant, and the sequence will be repeated. Initially, 3 patients will be enrolled:
 - o If 0/3 or 1/3 patients present with a DLT, another 3 patients will be enrolled.
 - If 0/6 or 1/6 patients present with a DLT, the safety lead-in phase will conclude and enrollment will continue to a total of 28 patients treated with TAS-120 (16 mg QD) plus fulvestrant.
 - If ≥2/3 or ≥2/6 patients present with a DLT at the dose of TAS-120 at 16 mg QD plus fulvestrant, the assessment of the combination and further enrollment to Cohort 4 will be discontinued.

[figure not shown]

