5.3. Dose and Schedule Modifications

5.3.1. Dose and Schedule Modifications for TAS-120

5.3.1.1. General Considerations

This section defines general dose modification guidelines for patients receiving TAS-120 in any cohort. For detailed discussion of TAS-120 dose modification in Cohort 4 in the setting of a DLT, see Section 3.1.

In Cohort 4, in cases where a toxicity cannot be clearly attributed to either drug (TAS-120 or fulvestrant), TAS-120 should be modified or discontinued first.

The starting dose of TAS-120 is

- 20 mg QD for all patients in Cohorts 1-3
- 16 or 20 mg QD in Cohort 4, depending on the observations in the safety lead-in (Section 3.1).

Dose reduction to a minimum dose of 12 mg QD is permitted, with available dose levels of 16 mg QD and 12 mg QD.

If dose reduction fails to result in achieving minimal criteria to resume treatment, or if toxicities occur which would necessitate reduction of the dose of TAS-120 below 12 mg QD, the patient should be discontinued from TAS-120.

If the TAS-120 dose is reduced, the dose will not be increased upon resumption. If a benefit/risk assessment favors the increase of dose up to the initial starting dose after dose reduction, an agreement with the Sponsor's Medical Monitor is required prior to the dose increase.

If toxicities requiring dose reduction do not recover based on the criteria defined in Table 4 through Table 6 within 28 days after the last dose of TAS-120, the patient will be discontinued permanently from the study (Section 4.4). If resumption criteria are met within 28 days of the last dose of TAS-120, the patient may resume TAS-120 treatment at the appropriate dose level.

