5.3.1.3. Dose Modifications for Hematologic Toxicities

Criteria for dose interruption and resumption for hematologic toxicities are presented in Table 6.

Table 6: TAS-120 Dose Interruption and Modification Criteria for Related Hematologic Toxicities

Worst toxicity	Recommended dose modification any time during a cycle
CTCAE Grade (value)	of TAS-120
Anemia (Hgb)	
Grade 1 (Hgb < LLN - 10.0 g/dL)	Maintain dose level
Grade 2 (Hgb $< 10 - 8.0 \text{ g/dL}$)	Maintain dose level
Grade 3 (Hgb < 8.0 - 6.5 g/dL)	Withhold dose until resolved to \leq Grade 1 or baseline,
	 If resolved ≤7 days, then maintain dose level
	• If resolved >7 days, then reduce 1 dose level
Grade 4 (life threatening consequences; urgent intervention indicated)	Withhold dose until resolved to \leq Grade 1 or baseline, then reduce 1 dose level
Neutropenia (ANC)	
Grade 1 (ANC < LLN - 1500/mm ³)	Maintain dose level
Grade 2 (ANC < 1500 - 1000/mm ³)	Maintain dose level
Grade 3 (ANC $< 1000 - 500/\text{mm}^3$)	Maintain dose level
Grade 4 (ANC < 500/mm ³)	Withhold dose until resolved to \leq Grade 2 or baseline,
	 If resolved ≤7 days, then maintain dose level
	• If resolved >7 days, then reduce 1 dose level
Febrile neutropenia (ANC < 1000/mm ³ , fever ≥ 38.5°C)	Withhold dose until resolved, then reduce 1 dose level
Thrombocytopenia	
Grade 1 (PLT < LLN - 75,000/mm ³)	Maintain dose level
Grade 2 (PLT < 75,000 - 50,000/mm ³)	Maintain dose level
Grade 3 (PLT < 50,000 - 25,000/mm ³)	Withhold dose until resolved to \leq Grade 1 or baseline,
	• If resolved ≤7 days, then maintain dose level
	• If resolved >7 days, then reduce 1 dose level
Grade 4 (PLT < 25,000/mm ³)	Withhold dose until resolved to ≤ Grade 1 or baseline, then
	reduce 1 dose level

Abbreviations: ANC=absolute neutrophil count; CTCAE=Common Terminology Criteria for Adverse Events; Hgb=hemoglobin; LLN=lower limit of normal; PLT=platelets.

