Sample size considerations for **Cohort 4** (primary endpoint 6-month PFS) are based on a proof-of-concept Phase 2 design, differentiating a null 6-month 25% PFS rate with a target rate of 50%. Approximately 28 patients will be treated. It has approximately 80% power to reject the null hypothesis that the true 6-month PFS rate is \leq 25%, considering a 1-sided alpha (type 1 error rate) of 5%. In addition, 6-12 patients will be enrolled as a safety lead-in. The patients in the safety lead-in who are treated at the recommended Phase 2 dose will be included in the main cohort of 28 patients. Thus up to 34 patients may be enrolled for this cohort.

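### Cohort 4 lead-in: a febrile neutropenia that Table 3 counts as a DLT can sit below Table 6's fever threshold, where the recommended action is to leave the TAS-120 dose unchanged

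*Protocol*

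**What the plan says.** Protocol Section 5.2, Table 3, defines DLTs for the Cohort 4 safety lead-in in Cycle 1, for events not clearly due to an extraneous cause. Febrile neutropenia qualifies at ANC below 1000/mm³ "with a single body temperature of >38.3°C [101°F] or a sustained temperature of ≥38°C [100.4°F] for more than 1 hour", provided antibiotics have to be started.

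Protocol Section 5.3.1.3, Table 6, gives dose modifications for related hematologic toxicities. Its action column is headed "Recommended dose modification any time during a cycle". Its febrile-neutropenia row requires ANC below 1000/mm³ and fever of at least 38.5 °C, with the action "Withhold dose until resolved, then reduce 1 dose level". Its row for Grade 3 neutropenia (ANC 500 to <1000/mm³) keeps the dose as it is.

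Protocol Section 5.3.1.1 applies these guidelines to every cohort and adds: "For detailed discussion of TAS-120 dose modification in Cohort 4 in the setting of a DLT, see Section 3.1". It also says that when a Cohort 4 toxicity cannot be clearly assigned to one of the two drugs, "TAS-120 should be modified or discontinued first".

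Section 3.1 gives the lead-in decision rule. After two or more DLTs at 20 mg, "Subsequent patients will be treated at a dose of TAS-120 of 16 mg QD plus fulvestrant". It does not say what happens to the patient who had the DLT. The SAP counts DLTs by dose level (Section 6.5.2.7) and adds nothing on managing the individual patient.

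**The concern.** The two tables use different fever thresholds for the same diagnosis. In the gap between them, an event serious enough to count against the combination dose carries a recommendation to continue that dose in the patient who had it.

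At stake is the safety of individual patients in the lead-in, who are the first to receive TAS-120 with fulvestrant. An investigator who looked only at the table row would neither hold nor reduce TAS-120 in a neutropenic, febrile patient on antibiotics. The cross-reference that appears to cover this situation leads to a section with no rule for that patient.

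**Working it through.** No plan figure needs reproducing; the check is a comparison of the two rules.

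**Test case.** Cohort 4 lead-in, Cycle 1, related event, ANC 500 to <1000/mm³, antibiotics started, single reading of 38.4 °C.

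| Step | Rule | Result |
|---|---|---|
| Table 3, single reading | 38.4 > 38.3 | true: DLT |
| Table 6, febrile-neutropenia row | 38.4 ≥ 38.5 | false: row not met |
| Table 6, Grade 3 neutropenia row | ANC 500 to <1000/mm³ | met: dose unchanged |

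**Extent of the gap.** For a single reading it runs from above 38.3 to below 38.5 °C. For a temperature sustained for more than 1 hour it runs from 38.0 to below 38.5 °C, because Table 6 has no sustained-temperature criterion. From 38.5 °C upward both tables recognise the event. Below ANC 500/mm³ the Grade 4 neutropenia row already withholds TAS-120, so no such patient is told to continue through the event. There, only the later reduction can differ, since that row restores the same dose if the neutropenia resolves within 7 days.

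**Is there another patient-level instruction?** Section 5.3.1.1 points to Section 3.1, whose dose rule concerns subsequent patients. The specific instruction for the affected patient is therefore Table 6.

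**Is the mismatch typical of the two tables?** The other hematologic DLTs in Table 3, set against Table 6:

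- Grade 4 neutropenia for more than 7 days: withhold, then reduce.
- Grade 4 thrombocytopenia for more than 7 days: withhold, then reduce.
- Grade 3 or higher thrombocytopenia with bleeding: withhold, with reduction depending on grade and time to recovery.

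Each leads to at least a hold. Febrile neutropenia in the gap is the only hematologic DLT whose Table 6 action is to carry on unchanged.

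**Size of the dose difference.** At the first lead-in level TAS-120 stays at 20 mg instead of being held and resumed at 16 mg: (20 − 16)/20 = 20% lower. At the second level it stays at 16 mg instead of 12 mg: (16 − 12)/16 = 25% lower.

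**Patients exposed.** Section 10.1 says "6-12 patients will be enrolled as a safety lead-in". The documents give no incidence for febrile neutropenia. Section 1.2.2 does not name neutropenia among the frequent treatment-related events.

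**The case against.** The best case for leaving the text alone has four parts.

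1. **Different purposes.** Table 3 feeds a cohort-level decision and Table 6 guides individual care, and nothing says that every DLT must trigger a hold. Section 5.3.1.2 even lets an investigator keep the same dose for nonhematologic events of any grade, naming fatigue, although fatigue of Grade 3 or higher lasting a week is a DLT. This shows that the protocol tolerates some DLTs without a dose change. But that discretion is confined to nonhematologic events, and neither document gives a reason for two fever thresholds.
2. **General safeguards.** Section 8.4.1 requires out-of-range laboratory values to be evaluated for clinical impact before the next TAS-120 dose. Table 7 requires Grade 3 or higher neutropenia to be rechecked at least twice a week. Section 4.4 allows discontinuation for unacceptable events or by physician's decision. Table 6 itself only recommends, and the rule to modify TAS-120 first helps when attribution is unclear. All of this stands and makes harm less likely. None of it supplies a dose action for this event, and Table 7's reference to restarting treatment fits poorly with a row that never stops it.
3. **Narrow reach.** Several conditions must coincide within a band of a few tenths of a degree. This is conceded.
4. **Existing scope wording.** Section 5.3.1.1 already covers all cohorts, so Tables 4 to 6 arguably already govern the individual. That is the sensible reading, but the next sentence sends the reader of a Cohort 4 DLT elsewhere.

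**Conclusion.** The inconsistency is real and minor. It is confined to the Cohort 4 lead-in in Cycle 1, to related events with ANC 500 to <1000/mm³ and antibiotics started, and to the temperature gap shown above. Few patients, possibly none, would be affected. No efficacy figure, alpha or power depends on it. The conclusion rests on reading Section 3.1 as a rule for later patients only, which is what its wording supports.

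A reader might infer three stronger things that the documents do not support.

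- **That 38.5 °C is wrong throughout Table 6.** Cohorts 1 to 3 have no DLT definition, so nothing there conflicts. Importing Table 3's temperatures without its antibiotic condition would also impose a hold and reduction on events that are not DLTs.
- **That the lead-in dose decision is distorted.** The event is counted as a DLT under Table 3 whatever Table 6 recommends, so the DLT count is unaffected.
- **That the patient is left unprotected.** The general safeguards and the advisory heading apply; what is missing is a specific action consistent with the DLT status.

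**What to change.** Two wording changes in the next amendment:

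1. A footnote to the febrile-neutropenia row of Table 6: in the Cohort 4 safety lead-in, any event meeting the full Table 3 febrile-neutropenia definition, including the start of antibiotics, is managed under this row (TAS-120 withheld until resolution, then reduced by one level).
2. A clarification in Section 5.3.1.1: Section 3.1 sets the dose for subsequent patients, and Tables 4 to 6 govern the individual patient who had the DLT.

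The cost is one footnote and one sentence. The downside is possibly an occasional extra hold and reduction in a lead-in patient, and under Section 5.3.1.1 a reduced dose is not raised again without the Medical Monitor's agreement. The footnote adds no DLTs, because it applies only to events that already are DLTs. Nor does it remove patients from the DLT Evaluable Set, because Section 10.3 excludes for low cumulative TAS-120 dose only when the reason is something other than a DLT.
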